Study Protocol and Statistical Analysis Plan

Evaluate the Benefit of a BiCROS Hearing Aid Fitting – ID# 461

October 3rd, 2022

NCT05379231

Evaluate the Benefit of a BiCROS Hearing Aid Fitting – ID# 461

1 Objectives and hypotheses of the clinical investigation

1.1 Purpose of the clinical investigation claims for clinical performance, effectiveness or safety of the investigational device that are to be verified

This study will be a PMCF study in order to substantiate the clinical benefit of a BiCROS system (regulatory requirement) and to secondly substantiate intended claims.

1.2 Primary and Secondary Objectives

The **primary objective** of this study is to evaluate whether a BiCROS fitting improves Speech Intelligibility for speech from the front and noise from the better ear's side compared to no treatment (unaided) for adults with unaidable hearing loss in one ear and aidable hearing loss in the other ear measured with the US Matrix Test.

The **secondary objectives** of this study are:

1. Evaluate whether a BiCROS fitting improves Speech Intelligibility in a setup with speech from the front and noise from the better ear's side compared to the alternative treatment of a monaural hearing aid fitting for adults with unaidable hearing loss in one ear and aidable hearing loss in the other ear measured with the US Matrix Test.
2. Evaluate whether a BiCROS fitting improves Speech Recognition Thresholds (SRT) by 1dB for speech from front in diffuse noise compared to no treatment (unaided) for adults with unaidable hearing loss in one ear and aidable hearing loss in the other ear measured with the US Matrix Test.
3. Evaluate whether a BiCROS fitting improves Speech Intelligibility in diffuse noise compared to the alternative treatment of a monaural hearing aid fitting for adults with unaidable hearing loss in one ear and aidable hearing loss in the other ear measured with the US Matrix Test.
4. Evaluate whether a BiCROS fitting results in improved subjective quality of hearing compared to no treatment (unaided) for adults with unaidable hearing loss in one ear and aidable hearing loss in the other ear measured with a questionnaire (SSQ).
5. Evaluate decrease in subjective listening effort for adults with unaidable hearing loss in one ear and aidable hearing loss in the other ear with a BiCROS fitting compared to no treatment (unaided) with a questionnaire or other means.

2 Design of the clinical investigation

2.1 General

2.1.1 Design Type

This clinical investigation is an interventional study, conducted at one investigation site, with a confirmatory design. The investigation employs a single group of participants that will be tested in all conditions (cross-over) and be blinded towards the intervention condition they are tested in as much as possible (unaided can't be blinded).

Test conditions:

- Experimental intervention: BiCROS fitting: A CROS microphone transmitter is worn on the poorer, unaidable ear and the hearing aid on the better hearing ear.
- Control intervention: Monaural hearing aid fitting: One hearing aid is worn on the better hearing ear.
- Control intervention: BiCROS fitting: A CROS microphone transmitter (with omnidirectional microphone mode) is worn on the poorer, unaidable ear and the hearing aid (with omnidirectional mode) on the better hearing ear.
- Control intervention: Monaural hearing aid fitting: One hearing aid (with omnidirectional mode) is worn on the better hearing ear.
- No intervention: No treatment (unaided), i.e. no CROS transmitter and no hearing aid are worn. (Condition not included in preference ratings because it doesn't allow for quick AB comparisons.)
- The order of conditions will be randomized.

2.2 Procedures

2.2.1 Investigation-related Procedure

Hearing test, ear Impression taking, hearing aid fitting, and outcome measures will be performed according to Table 1. The aforementioned parts of the procedures except for outcome measures may be conducted at Sonova Innovation Centre Toronto in Mississauga for participants who wish to receive fitting closer to their home to reduce the amount of travel to the London study site. The study team will be present in person for the initial hearing aid fitting. For those participants, in-between visits during the home trial period, which may be required for fine tuning, will be conducted in Mississauga, too, where a remote connection to the study team in London will be established by a Sponsor employee that is not otherwise taking part in this study. This way, the audiologist who fitted the hearing aids will be able to orchestrate the fine tune to not introduce any additional variability between fittings.

All outcome measurements will be solely conducted at the National Centre for Audiology in London.

Study Visits

Table 1 Overview of study visits

Visits	Tests and Procedures
Visit 1 Approximately 2 hours	
• Hearing Test under the supervision of a registered audiologist.• Impressions for both ears if required.• If impressions are not required, the hearing aid fitting described in Visit 2 will begin.
Visit 2 Approximately 2 hours	
Hearing Aid Fitting
 
• Hearing Aid fitting under the supervision of a registered audiologist.

	
 • Probe microphone measure to ensure hearing aid is fitted properly.
Home Use	
Participants will be asked to wear the BICROS hearing aid system home to use for 4-5 weeks.
 
Participants may schedule visits to see the study audiologist if you require any adjustments during that time.
 
Participants will be given two questionnaires and asked to complete them prior to returning to the lab for the next visit.

Visit 3 & Visit 4 (if necessary) Up to 2 hours each	
In-lab Assessments:
 
 • Rating the sound quality of speech and music. • Rating the amount of effort required to listen to speech in noise without the BICROS system and while wearing the BICROS system in different hearing aid settings. • Indicating preference between different hearing aid settings for speech • Repeating speech back in quiet and in noise. • We will ask participants for their opinions of the BICROS hearing aid and document these opinions using a structured process. • Return devices to study audiologist. • Sounds will be delivered by hearing aid, headphone and speakers below uncomfortable levels. • An end of study assessment of hearing levels and ear canal status (audiometry, otoscopy) will be completed.

3 Statistical design and analysis

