3.2.3 Secondary Endpoint Analysis

Whether there is a significant benefit of the BiCROS fitting over the unaided condition in terms of SRTs will be tested using a one-tailed paired samples t-test. The assumption of normally distributed paired differences between unaided and BiCROS will be tested by visually inspecting Q-Q plots, checking skewness and kurtosis against predefined thresholds (skewness < 0.8 and kurtosis < 2) and testing for statistically significant deviations from normality ($p < .05$) using the Shapiro-Wilk-test. Outliers will be defined as differences that lie outside the range between 1.5 times the interquartile range below the first quartile and 1.5 time the interquartile range above the third quartile of the data. Outliers will be removed if they are ≥ 2 standard deviations from the mean. In case of a non-normal distribution, non-parametric testing will take place with a one-sided Wilcoxon rank sum test.

Descriptive analysis with mean and standard deviations will be completed for the questionnaire results. In addition, repeated measures ANOVA with follow-up post hoc t-tests with Bonferroni correction as required will be performed comparing the responses of multiple sub-scales to 0 ("unchanged" - the questionnaire asks participants to rate their experience in terms of change (improvement vs. no improvement for each question) including an option for no change). Factors are conditions (unaided and BiCROS) and SSQ subscales (speech hearing, spatial hearing, and qualities of hearing). Violations of sphericity will be corrected by adjusting the degrees of freedom of the ANOVA using the Greenhouse-Geiser epsilon.

Sound quality ratings and listening effort ratings will be analyzed using repeated measures ANOVA with follow-up post hoc t-tests with Bonferroni correction as required. Factors are conditions (unaided, monaural with omnidirectional and beamformer, and BiCROS with omnidirectional and beamformer) and subscales (clarity, total Impression, and listening effort).

Preference ratings will be analyzed using one-sample Shapiro-Wilk test for normality to detect any significant skew toward a preferred setting, using BiCROS beamformer as the test condition for all comparisons.

According to common standards and Type I error probability of 5% is deemed to be acceptable and the null hypothesis will be rejected if the p -value is equal to or less than 0.05.

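### The SSQ plan for objective 4 has no secured unaided comparator: no SSQ is scheduled before fitting, the change rating has no stated reference, and the condition factor in the ANOVA lacks its unaided level

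*Combined protocol and SAP*

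**What the plan says.** - **Objective (section 1.2, secondary objective 4).** "Evaluate whether a BiCROS fitting results in improved subjective quality of hearing compared to no treatment (unaided"), measured with the SSQ. Section 2.1.1 defines the comparator: "No treatment (unaided), i.e. no CROS transmitter and no hearing aid are worn".
- **Schedule (section 2.2.1, Table 1).** Visit 1 lists a hearing test and ear impressions, and it may run straight into fitting: "If impressions are not required, the hearing aid fitting described in Visit 2 will begin". Visit 2 is the fitting. Neither visit lists a questionnaire. The Home Use row states "Participants will be asked to wear the BICROS hearing aid system home to use for 4-5 weeks" and then "Participants will be given two questionnaires and asked to complete them prior to returning to the lab for the next visit". The two questionnaires are not named. The in-lab list for Visits 3 and 4 does not mention the SSQ.
- **Analysis (section 3.2.3).** The plan explains that "the questionnaire asks participants to rate their experience in terms of change", with an option for no change, and compares subscale responses with 0, meaning unchanged. The next sentence gives the ANOVA two factors: condition, with levels unaided and BiCROS, and SSQ subscale, with three levels.

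**The concern.** Objective 4 is a contrast between two states, BiCROS and no device. It can be measured in two ways: rate each state and take the difference, or ask directly for the change from one state to the other. The second way works only if the form fixes the starting state. Section 3.2.3 uses parts of both and completes neither. It does not say what the change is rated from, and it asks for a condition factor whose unaided level has no scheduled source.

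Section 2.1.1 calls the study confirmatory, and section 1.1 says it is also meant to support intended claims. A statement that BiCROS improves subjective hearing over unaided would rest on a reference that the plan does not define, and on an analysis that the analyst would have to redesign after seeing the data.

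**Working it through.** The documents give no SSQ effect size, SD or sample size, so there is no stated figure to reproduce. The check sets the schedule against the analysis.

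**Step 1: what each part of section 3.2.3 needs.**
- Test against 0: one change score per person and subscale, with unaided as the reference if it is to answer objective 4.
- Condition × subscale ANOVA: two SSQ scores per person and subscale, one for unaided and one for BiCROS, so 2 × 3 = 6 values per person.

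**Step 2: what Table 1 can supply under each reading of the two unnamed questionnaires.**

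| Reading | Test against 0 | Condition factor | Objective 4 answered? |
|---|---|---|---|
| One SSQ change form plus some other questionnaire | Possible (3 values per person) | No unaided level | Only if the form's reference is no device |
| Two SSQ forms, one rating unaided and one rating BiCROS | 0 does not mean unchanged on such forms | Possible (6 values) | Yes, but both are completed after fitting, and this contradicts the description of a change rating |
| Two change forms, one per condition | Unclear | Change for the unaided state has no defined meaning | No |

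Under no reading do both parts of the paragraph have the data they need.

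**Step 3: comparison with listening effort.** Table 1 has effort rated in the lab both without the BiCROS system and with it, and section 3.2.3 gives that analysis an unaided level. For effort, schedule and model agree. For the SSQ they do not.

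**Step 4: what an unfixed reference could do (assumption only).** Let B be the mean SSQ benefit of BiCROS over unaided. Suppose a share p of participants rate change from a device they already own, and that device gives a fraction q of B. Assume B is the same in users and non-users.

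Mean change = (1 − p)·B + p·(B − q·B) = B·(1 − p·q)

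- p = 0: 1 − 0 = 1.00, no distortion.
- p = q = 0.25: 1 − 0.0625 = 0.9375, or 94% of B.
- p = q = 0.50: 1 − 0.25 = 0.75, or 75% of B.
- p = q = 0.75: 1 − 0.5625 = 0.4375, or 44% of B.

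Neither p nor q is in the documents. The range gives the direction (towards understatement) and shows that the size is open. It is not an estimate for this trial.

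**The case against.** **The form may already name its reference.** Its wording is not in the documents. It may say that the comparison is with no device, in which case the test against 0 answers objective 4. This stands. A reader might infer that the form measures change from a prior aid, but nothing in the documents says so. The defect is that the plan does not fix the reference, not that a wrong one is known to be used.

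**Prior users may not be enrolled.** The documents contain no eligibility criteria, so silence on prior device use shows neither inclusion nor exclusion. This also stands, and it is why Step 4 is conditional.

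**An unaided SSQ may be intended.** The condition factor suggests one, and one of the two questionnaires could be it. This is possible, so it cannot be said that the SSQ is given only once. But such a form would be answered during BiCROS wear, and it would conflict with the change rating described in the same paragraph.

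**The unaided level could be filled with zeros.** An analyst could set unaided to 0 for everyone. The condition effect would then only repeat the test of mean change against 0. The plan does not say to do this, and it presupposes that the reference is no device.

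**Loss of power.** A reader might turn the Step 4 range into a power loss at the 19 participants of section 3.1. The documents do not support that. The 19 is for the primary comparison, no SSQ effect is stated, and the SSQ analysis is a repeated-measures ANOVA with Bonferroni-corrected follow-up tests, not one paired t-test.

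**Low stakes.** The primary endpoint uses Matrix test SRTs and is untouched, listening effort gives a separate subjective comparison with unaided, and the likely error is conservative. All true. This limits the severity but does not remove the inconsistency.

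**Conclusion.** The point holds as an inconsistency between objective, schedule and analysis. Three facts are firm: Table 1 lists no questionnaire before fitting, the reference for the change rating is not stated, and a change score tested against 0 cannot supply the two-level condition factor in the same paragraph. The SSQ analysis therefore cannot be run as written, and the unaided comparator of objective 4 is not secured.

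Any bias is conditional. It needs participants who already use a device and who rate change from it. If both hold, benefit over unaided would probably be understated; the amount cannot be estimated from the documents. The point concerns one secondary objective and is worth correcting because correction is cheap.

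**What to change.** **Preferred.** Add the SSQ to Visit 1 in Table 1, before any fitting (which may begin at that visit), answered for listening with no device. Repeat it at the end of home use, after the final adjustment, answered for BiCROS. In section 3.2.3, analyse the within-person difference by subscale in the condition × subscale model, and delete the test of change scores against 0.

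**Alternative.** Keep the change form and print on it that the comparison is with listening without any hearing device. Delete the condition factor and test the subscale change scores against 0.

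**In either case.** Name the two questionnaires in Table 1, state when they are to be completed, record prior device use at Visit 1, and report SSQ results by prior use descriptively.

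**Cost.** The preferred version adds one questionnaire at an existing visit of about two hours, plus edited instructions. Existing device users must judge unaided listening from experience without their aid, which is a real weakness and a reason to report by prior use. Section 2.2.1 allows Visit 1 procedures in Mississauga but keeps outcome measurement in London. The home-use questionnaires already sit outside that rule, so one sentence exempting questionnaires would settle it. The alternative adds no questionnaire but still relies on recall of unaided listening.

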3.1 Determination of Sample Size

Primary objective

A power analysis was conducted to apply a one-tailed paired samples t-test to compare the difference between the two conditions tested in the primary objective. The required sample size for 95% power with a one-tailed paired t-test is 19.

With additional 4 participants as backup (based on previous research experience), the required number of participants is 23. For 80% power, 12 participants are needed.

Statistical criteria of termination of trial

There are no statistical criteria for stopping the study.

3.2 Planned Analyses

3.2.1 Datasets to be analyzed, analysis population

Dataset will be the SNRs from the Matrix test across hearing aid conditions, questionnaire responses, subjective rating values, listening effort ratings, and preference ratings.

3.2.2 Primary Endpoint Analysis

Whether there is a significant benefit of the BiCROS fitting over the unaided condition in terms of SRTs will be tested using a one-tailed paired samples t-test. The assumption of normally distributed paired differences between unaided and BiCROS will be tested by visually inspecting Q-Q plots, checking skewness and kurtosis against predefined thresholds (skewness < 0.8 and kurtosis < 2) and testing for statistically significant deviations from normality ($p < .05$) using the Shapiro-Wilk-test. Outliers will be defined as differences that lie outside the range between 1.5 times the interquartile range below the first quartile and 1.5 time the interquartile range above the third quartile of the data. Outliers will be removed if they are ≥ 2 standard deviations from the mean. In case of a non-normal distribution, non-parametric testing will take place with a one-sided Wilcoxon rank sum test.

According to common standards, a Type I error probability of 5% is deemed to be acceptable and the null-hypothesis will be rejected if the p -value is equal to or less than 0.05.

Time point of analysis: After all data collection of the primary endpoint is completed for all participants.

Responsibility for analysis: Western University investigators will complete the statistics.

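### The SRT test is chosen from the observed differences by several normality checks with no rule for conflicts; naming the paired t-test outright would remove that choice and a small loss of power

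*Combined protocol and SAP*

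**What the plan says.** Section 3.2.2 states that the benefit of BiCROS over unaided "in terms of SRTs will be tested using a one-tailed paired samples t-test", and that "the null-hypothesis will be rejected if the p -value is equal to or less than 0.05". The same paragraph then makes the test conditional on the shape of the paired differences, judged in three ways:

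- a plot: "The assumption of normally distributed paired differences between unaided and BiCROS will be tested by visually inspecting Q-Q plots";
- numeric cut-offs: skewness below 0.8 and kurtosis below 2;
- a significance test at p < .05, "using the Shapiro-Wilk-test".

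The consequence is stated as: "In case of a non-normal distribution, non-parametric testing will take place with a one-sided Wilcoxon rank sum test".

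The plan does not say which check decides, how many must fail, or what Q-Q pattern counts as non-normal. It does not say whether the skewness cut-off is on the absolute value, or whether kurtosis is raw or excess. The order of these checks and the outlier deletion in the same paragraph is also open. Section 3.2.3 repeats the text for the secondary SRT analysis, including "testing for statistically significant deviations from normality". Section 3.1 sizes the study for the paired t-test only: 19 participants for 95% power, 12 for 80%, and 23 with backups. Section 2.1.1 calls the design confirmatory.

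**The concern.** In a confirmatory trial the test behind the primary p-value should be fixed before the outcome is seen. Here it is settled afterwards, from the same differences that are being tested, and one of the checks is a visual judgement. Where the checks disagree, two careful analysts could follow the text and report p-values from different tests.

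The two tests also differ in what they examine. The paired t-test concerns the mean difference. The rank sum test is for two independent samples and ignores the pairing, so a switch to it discards the precision that the within-subject design was meant to provide. A signed-rank test would keep the pairing, but with asymmetric differences it does not test the mean. At stake are the power stated in section 3.1, the error rate of the primary claim, and how clearly the result can be defended as pre-specified.

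**Working it through.** **1. The plan's own figure.** Section 3.1 gives no effect size or SD, so N cannot be derived from stated inputs. It can be back-solved. For a one-sided paired t-test, power = P(T > t(0.95, n-1)), where T is noncentral t with n-1 degrees of freedom and noncentrality dz × √n.

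- n = 19, dz = 0.79: noncentrality 0.79 × √19 = 3.44, critical value 1.734, power 95.2%.
- n = 12, dz = 0.79: noncentrality 0.79 × √12 = 2.74, critical value 1.796, power 82.1%.

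A dz of about 0.785 to 0.806 yields both N = 19 and N = 12, so the two stated sample sizes agree with each other. I use dz = 0.79.

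**2. Set-up of the simulation.** Differences are signed so that positive means BiCROS is better. They are normal, or centred gamma with skewness -1 or +1, and the null is a mean difference of zero. I read the cut-offs as absolute skewness and excess kurtosis. On the raw scale (normal = 3) about 90% of normal samples at n = 19 would fail a cut-off of 2, so that reading is unlikely to be intended. No outlier deletion is applied and the Q-Q judgement is not simulated. Skewness and within-pair correlation are assumptions, because the documents give neither.

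**3. How often the numeric checks disagree (n = 19).**

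| Counting | Normal | Skewness of size 1 |
|---|---|---|
| Skewness/kurtosis as one block against Shapiro-Wilk | about 10-11% | about 20% |
| Skewness, kurtosis and Shapiro-Wilk separately | about 12% | about 31% |

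**4. Type I error (n = 19, nominal one-sided 5%, 20,000 samples per row).** The rank sum ranges cover correlations of about 0.3 to 0.8. In each gated column, the first entry lets Shapiro-Wilk govern and the second switches if any numeric check fails.

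| Differences | t-test alone | Rank sum fallback (as written) | Signed-rank fallback |
|---|---|---|---|
| Normal | 5.0% | 4.7-4.8%; 4.2-4.6% | 5.0%; 5.1% |
| Skewness -1 | 7.7% | 6.3-7.2%; 5.0-6.6% | 9.6%; 10.2% |
| Skewness +1 | 3.1% | 2.6-2.9%; 2.2-2.7% | 2.8%; 2.6% |

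A separate run at correlation 0.5 gave the same picture. At skewness -1 it gave 7.4% for the t-test, 5.6-6.5% with the rank sum fallback and 9.6-10.0% with signed-rank. At +1 it gave 3.0% for the t-test and 2.6-2.8% with signed-rank.

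**5. Effect of the missing conflict rule on error.** With a signed-rank fallback at n = 19 and skewness -1, switching only if all numeric checks fail gives 9.4%, and switching if any fails gives 10.2%: a gap of 0.8 points. Taking the smaller p-value in every conflict gives 10.3%, and 5.2% under normality. At n = 23 the all/any gap at skewness -1 is 10.9 - 9.6 = 1.3 points.

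**6. Power with the fallback as written (normal differences, dz = 0.79, n = 19).** The rank sum test used alone has power of about 81% at correlation 0.5 and 60% at 0.7, against 95% for the paired t-test. Gating to it only in flagged samples dilutes that loss:

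| Correlation | t-test alone | Gated to rank sum |
|---|---|---|
| 0.5 | 95% | about 93-94% |
| 0.7 | 95% | about 90-93% |

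The upper ends apply if Shapiro-Wilk governs, the lower ends if any failed check triggers the switch. Power falls further under skew, where switching is more frequent.

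**The case against.** The plan is not silent. The skewness and kurtosis cut-offs, the Shapiro-Wilk level, the direction and the fallback test are all fixed in advance, so only part of the decision is open. Under normality the gate leaves error at about 5%. The choice of governing check moves error by less than one point at n = 19, and by little more at n = 23. All of this stands, and it keeps the severity low.

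A reader might infer that the pre-test raises type I error whenever the differences are skewed. The documents do not support that. With the rank sum test that the plan names, gated error is below that of the t-test alone in every skewed scenario tried. The rise appears only if the fallback is replaced by a signed-rank test, and then only when the long tail points to BiCROS being worse; with the opposite skew both procedures are conservative. Neither the direction nor the size of any skew is given in the documents. It would also be wrong to pair the signed-rank error figures with the rank sum power loss, since they belong to two different plans.

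Finally, dropping the gate does not bring error to 5% under skew: part of the departure belongs to the t-test itself. Part of the signed-rank excess also reflects a null defined on the mean, which the paired t-test implies but the objectives do not spell out.

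What remains is that the primary test is undetermined until the outcome is seen, and that the route away from the paired t-test costs some of the power on which the sample size rests.

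**Conclusion.** The point holds as a low-severity matter of specification. The test for the SRT endpoints depends on the observed differences, one check is visual, and no rule settles disagreements that would be common at this sample size.

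Taken as written, the cost is mainly power: about 1 to 2 points at correlation 0.5 and 2 to 5 points at 0.7 under normal differences, with type I error not above that of the t-test. If a signed-rank test is meant, error is about 10% against 7.5% for the t-test at skewness -1, and below the t-test's 3% at +1. A general claim that the gate inflates type I error is not supported, nor is a claim that the missing rule lets analysts move the error rate far.

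These sizes rest on the back-solved dz of 0.79, the assumed skewness and correlations, n = 19, a zero-mean null, absolute skewness and excess kurtosis, no outlier deletion, and no simulation of the Q-Q judgement.

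**What to change.** In section 3.2.2, name the one-tailed paired t-test as the single primary analysis whatever the normality checks show. Report the one-sided Wilcoxon signed-rank test as a pre-specified sensitivity analysis, in place of the rank sum test. Keep the Q-Q plots, skewness, kurtosis and Shapiro-Wilk result as description that does not alter the test. Make the same change for the SRT analysis in section 3.2.3.

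This is SAP wording only: no extra data, visits or participants. It restores the test on which section 3.1 bases its 95% power. There are two drawbacks to accept openly. Some efficiency is lost if the differences are heavy-tailed. The t-test also does not hold exactly 5% under skew (about 7.5% at skewness -1 and 3% at +1), so the descriptive checks and the signed-rank result should be shown beside it. Label: cheap improvement.

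### The non-parametric fallback in sections 3.2.2 and 3.2.3 is an independent-samples test (Wilcoxon rank sum), but the SRTs are paired; the signed-rank test should be named instead

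*Combined protocol and SAP*

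**What the plan says.** Section 2.1.1 describes one group in which each participant is tested under all conditions. Section 3.1 sizes the trial on a paired test: "The required sample size for 95% power with a one-tailed paired t-test is 19". It then adds four people as backup: "the required number of participants is 23. For 80% power, 12 participants are needed".

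Section 3.2.2 says that the BiCROS benefit over unaided "in terms of SRTs will be tested using a one-tailed paired samples t-test". On the normality check it says: "The assumption of normally distributed paired differences between unaided and BiCROS will be tested by visually inspecting Q-Q plots". It adds skewness and kurtosis limits and a Shapiro-Wilk test, and it defines outliers as differences too. If the check fails, the plan changes test: "In case of a non-normal distribution, non-parametric testing will take place with a one-sided Wilcoxon rank sum test". Section 3.2.3 repeats this paragraph for the secondary SRT analysis, including the fallback. Both sections declare a 5% type I error. The signed-rank test is named nowhere.

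**The concern.** The rank sum test compares two independent groups. Here both SRTs come from the same person, so the test ignores the pairing on which the sizing, the main test, the normality check and the outlier rule all rest. The paired counterpart is the Wilcoxon signed-rank test.

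Two things are at stake. First, an analyst who follows the text runs a test whose error rate is not the stated 5% and to which the 95% power does not apply. Second, an analyst who sees the slip and runs signed-rank departs from the written plan after the data are in. The two tests can disagree on the same data, so the wording leaves a choice of p-value open on the primary endpoint. Section 2.1.1 calls the design confirmatory, and section 1.1 gives substantiation of clinical benefit as a regulatory requirement.

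**Working it through.** **Inputs.** From section 3.1: n = 19 for 95% power, n = 12 for 80%, planned n = 23, one-tailed paired t-test. From section 3.2.2: alpha 0.05. Not given: effect size, SD of the differences, within-person correlation rho. The first two are back-solved as a standardised paired effect, dz = mean difference / SD of differences. Rho is varied.

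**Step 1: the plan's own figures.** Power = P(T > t(0.95; n-1)), where T is noncentral t with n-1 degrees of freedom and noncentrality dz × √n. The smallest n for 95% is 19 if dz lies in 0.785-0.809. The smallest n for 80% is 12 if dz lies in 0.766-0.806. Both hold for dz 0.785-0.806; 0.795 is used below. It gives 94.4% at n = 18, 95.4% at 19, 79.0% at 11, 82.5% at 12 and 98.0% at 23. The two stated sizes are therefore consistent with each other, although the effect behind them cannot be checked.

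**Step 2: why pairing matters.** With common SD σ, the variance of the difference in condition means is 2σ²(1-rho)/n. An independent-samples test assumes 2σ²/n. For large n the rank sum type I error is then approximately 1 - Φ(1.645/√(1-rho)):

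- rho -0.3: 1.645/1.140 = 1.443, giving 7.4-7.5%
- rho 0: 5.0%
- rho 0.5: 1.645/0.707 = 2.326, giving 1.0%
- rho 0.8: 1.645/0.447 = 3.678, giving about 0.01%

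**Step 3: when the rank sum test is used.** Simulation with bivariate normal SRTs, one-sided 5%, dz 0.795 for power, 20,000 runs per setting:

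| rho | Type I error, n = 19 | Power, n = 19 | Power, n = 23 |
|---|---|---|---|
| 0 | 5.0% | 95% | 98% |
| 0.3 | 2.6% | 90% | 95% |
| 0.5 | 1.2% | 82% | 90% |
| 0.7 | 0.4% | 62% | 73% |
| 0.8 | 0.1% | 40% | 51% |

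At rho -0.3 and n = 19 the type I error is 7.1%. Signed-rank keeps type I error at about 5% and power at about 94% (n = 19) or 97% (n = 23) at every rho.

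**Step 4: the whole plan.** The fallback applies only if the check fails. The check is read here as failing if |skewness| ≥ 0.8, |excess kurtosis| ≥ 2 or Shapiro-Wilk p < .05; Q-Q inspection cannot be simulated. With truly normal differences it fails in about 14% of samples of 19 and 12% of samples of 23, or about 6% and 4% if run after outlier removal. Overall power (5,000-6,000 runs per setting):

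| rho | n = 19, check before removal | n = 19, after | n = 23, before | n = 23, after |
|---|---|---|---|---|
| 0 | 95.3% | 95.1% | 98.0% | 98.1% |
| 0.5 | 93.6% | 94.2% | 97.1% | 97.3% |
| 0.7 | 91.0% | 93.1% | 95.2% | 96.4% |
| 0.8 | 86.9% | 91.5% | 92.4% | 95.7% |

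With signed-rank as the fallback it is about 95-96% at n = 19 and 98% at n = 23.

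**Step 5: skewed differences, as an illustration.** With gamma (shape 4) differences, skewness 1, the check fails in about 46% of samples (22% after outlier removal). Overall power, check before removal, is 91% (rho 0.5) and 70% (rho 0.8) at n = 19, against 97% with signed-rank; at n = 23 it is 95% and 76%, against 99%. With the check after removal it is 91% and 82% at n = 19 (against 96%), and 95% and 86% at n = 23 (against 98%). The documents do not say how likely such skew is.

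**The case against.** The best defence is that this is a naming slip. Everything around the sentence is paired, and an analyst holding one column of differences cannot run a two-sample test on it. That is probably right about intent. But the analyst can go back to the two SRT columns, the sentence appears twice, and nothing in the documents corrects it.

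Second, the branch figures in step 3 overstate the effect on the trial. This stands. With normal data the whole-plan loss is at most about 2 percentage points up to rho 0.5, and at n = 23 power stays above 92% even at rho 0.8. The loss is material only with strong correlation or clearly non-normal differences.

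Third, the normality check was read with absolute values. On the literal wording, which limits only positive values, it fails less often: about 11% rather than 14% at n = 19, and 9% rather than 12% at n = 23. The difference is small.

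Fourth, positive correlation makes the error conservative, and nothing in the documents suggests negative correlation. This also stands.

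Fifth, signed-rank assumes symmetric differences under the null. In the gamma example with a true mean difference of zero, its one-sided type I error at n = 19 is about 2.0% or 10.5%, depending on the direction of skew. If no effect means that the two scores are exchangeable within a person, the differences are symmetric and the test is valid. This calls for a stated assumption; it does not favour the rank sum test.

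**Conclusion.** The concern holds. The fallback named for the primary endpoint and for the secondary SRT analysis is the wrong test for this design. That conclusion needs no assumption beyond the text.

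The size of the effect does rest on assumptions: dz back-solved to 0.795, an unknown within-person correlation, and one reading of the normality check. Positive correlation is the plausible case for repeated scores from one person, and the consequence is then lost power and a missed benefit. Type I error exceeds 5% only if the correlation is negative. The paired t-test branch is unaffected.

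The correction is still required, because the rule decides a confirmatory primary endpoint whenever the check fails, which is when the plan most depends on it.

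**What to change.** In sections 3.2.2 and 3.2.3, replace the rank sum test with the one-sided Wilcoxon signed-rank test on the within-participant differences, defined as unaided minus BiCROS. State that the test assumes differences symmetric about zero under the null.

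Some secondary objectives in section 1.2 assess BiCROS "compared to the alternative treatment of a monaural hearing aid fitting". Where the same test is used for those, the difference is monaural minus BiCROS. The SRT paragraph of section 3.2.3 mentions only the unaided comparison; that is a separate gap, and the new phrase alone does not close it.

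The cost is one phrase in two places plus a sentence on symmetry. No new data are needed and the sample size does not change. The change should be made before the data are analysed, so that the choice of test cannot depend on the result.
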